9.1.3 Secondary analyses

The analyses described above for the primary endpoint will be supplemented in a multivariate situation by a mixed linear regression model to take into account the covariates selected on the basis of the results of the univariate analysis and their clinical relevance. The practitioner effect will be measured and taken into account in the statistical analyses as a random effect. The results will be expressed in terms of regression coefficient and 95% confidence interval.

Comparisons between randomisation groups (group receiving only conventional massophysiotherapy, group receiving both conventional masso-physiotherapy and fasciatherapy and group receiving only fasciatherapy) concerning quantitative assessment criteria (functional assessment by the DALLAS self-assessment questionnaire, quality of life assessment by the SF-12 quality of life questionnaire, psychological assessment by the STAI Y questionnaire) will be carried out by Student's t-test or non-parametric Mann-Whitney test if the test conditions are met, assessment of quality of life using the SF-12 quality of life questionnaire, psychological assessment using the STAI Y questionnaire) will be carried out using Student's t test or the non-parametric Mann-Whitney test if the conditions of Student's test are not met (normality verified by the Shapiro-Wilk test and equality of variances by the Fisher-Snedecor test). Particular attention will be paid to the statistical distributions of the quantitative data under study. Where appropriate, the above analyses may be supplemented by more appropriate generalised linear regressions. The results will be expressed in terms of effect size and 95% confidence interval. In line with the recommendations proposed by Vickers and Altman, an ANCOVA-type analysis will also be proposed in order to compare the scores at the 5th session by adjusting for the values at the 1st session.

The STAI YB measuring anxiety status will be completed at the beginning and end of each session; the statistical analysis will therefore follow the same statistical analysis plan as that described for the primary endpoint.

Comparisons between the randomisation groups (conventional physiotherapy-only group, conventional physiotherapy and fasciatherapy group and fasciatherapy-only group) for categorical variables (e.g. functional assessment scores, quality of life assessment scores and psychological

assessment scores, categorised according to the statistical distribution or thresholds commonly reported in the literature) will be performed by chi-square test or Fisher's exact test. The results will be expressed in terms of absolute difference and 95% confidence interval. In multivariate situations, mixed generalized linear regression models (logit link function) will be considered. The results will then be expressed in terms of relative risk and 95% confidence interval.

Concerning the longitudinal analysis of categorical parameters (for example pain and STAI YB categorised according to statistical distribution or thresholds reported in the literature), the analysis will consider a mixed model approach for repeated data of the generalised linear type (logit link function for a binary dependent variable) making it possible to study the fixed effects of group, assessment time (session) and their interaction, while taking into account inter and intra patient variability (subject taken as a random effect), in addition to the (random) practitioner effect. The results will be expressed in terms of odds ratios and 95% confidence intervals.

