8.3.4 Archiving

The following documents will be archived by the name of the study at the FasciaFrance premises, under the responsibility of the coordinating investigator and FasciaFrance for 15 years after the end of the study.

These documents are :

- Protocol, observation book, any amendments,
- Original signed information forms and consents
- Individual data (authenticated copies of raw data)
- Follow-up documents
- Statistical analysis
- Final study report

At the end of the period of practical use, all documents to be archived will be placed under the responsibility of FasciaFrance.

No removal or destruction may be carried out without the agreement of the Developer. At the end of the 15 years, the Promoter will be consulted for destruction. All data, documents and reports may be subject to audit or inspection.

9 Statistical considerations

- 9.1 Data analysis method
 - 9.1.1 General

Statistical analysis will be carried out using Stata software (version 15, StataCorp, College Station).

Continuous variables will be presented in the form of mean and standard deviation, subject to the normality of their distribution (Shapiro-Wilk test if necessary). In the event of non-normality, they will be presented in the form of median, quartiles and extreme values. Qualitative variables should be expressed in terms of numbers and associated percentages. Wherever possible, graphical representations should be associated with these analyses.

Patients will be described and compared between groups (group receiving conventional physiotherapy only, group receiving both conventional physiotherapy and fasciatherapy and group receiving fasciatherapy only) at inclusion according to the following variables: compliance with eligibility criteria, epidemiological characteristics, clinical characteristics and characteristics of any treatments.

A description of protocol deviations, patients allocated according to these deviations and reasons for drop-out will also be provided. The number of patients included and the inclusion curve will be presented by randomisation group.

The initial comparability of the groups will be assessed on the main characteristics of the participants and potential factors associated with the primary endpoint. Any difference between groups on any of these characteristics will be determined on the basis of clinical and not just statistical considerations.

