Comparisons between randomisation groups will be made systematically (1) without adjustment (2) by adjusting for factors whose distribution could be unbalanced between groups.

All statistical tests will be carried out with a risk of error of the first kind α of 5%.

Part of the analyses concerning the secondary evaluation criteria should be mainly exploratory in nature. As discussed by several authors (*Bender, R.; Lange, S. Adjusting for multiple testing-When and how? J. Clin. Epidemiol. 2001, 54, 343-349; Feise, R.J. Do multiple outcome measures require p-value adjustment? BMC Med. Res. Methodol. 2002, 2, 8; Rothman, K.J. No adjustments are needed for multiple comparisons. Epidemiology 1990, 1, 43-46*), adjustment for the risk of error of 1st kind will not be proposed systematically, but on a case-by-case basis in the light of clinical and not purely statistical considerations.

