9.1.2 Main analysis

In order to evaluate the specific benefits of fasciatherapy compared with physiotherapy for chronic low back pain in terms of variation in pain before and after each of the 5 sessions considered in this protocol, the main analysis will consider a mixed model approach for repeated data, making it possible to study the fixed group effects (group receiving only conventional physiotherapy, group receiving both conventional physiotherapy and fasciatherapy and group receiving fasciatherapy only), assessment time (session) and their interaction, while taking into account inter- and intrapatient variability (subject taken as a random effect), in addition to the (random) practitioner effect. The results will be expressed in terms of regression coefficient and 95% confidence interval. It will also be proposed to study the difference between randomisation groups for each of the sessions. The results will be expressed in terms of effect size and 95% confidence interval.

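### The main pain model has no baseline pain covariate, and the adjusted versions of the primary comparison use covariates chosen after the data are seen

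*Combined protocol and SAP*

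**What the plan says.** Three places in the combined protocol and SAP bear on adjustment of the primary comparison.

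- **9.1.2 Main analysis.** Pain variation before and after each of the five sessions goes into a mixed model. Its fixed effects are group, "assessment time (session) and their interaction, while taking into account inter- and intrapatient variability (subject taken as a random effect"), with a random practitioner effect added. No baseline covariate appears.
- **9.1.1 General.** "Comparisons between randomisation groups will be made systematically (1) without adjustment (2) by adjusting for factors whose distribution could be unbalanced between groups". The factors are not listed. Baseline comparability is to be examined on the main participant characteristics and on factors possibly associated with the primary endpoint, and a difference between groups "will be determined on the basis of clinical and not just statistical considerations". No threshold is given.
- **9.1.3 Secondary analyses.** "The analyses described above for the primary endpoint will be supplemented in a multivariate situation by a mixed linear regression model", using "the covariates selected on the basis of the results of the univariate analysis", with clinical relevance as a further criterion. Again there is no list and no threshold.

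The only baseline adjustment that the plan names is an ANCOVA in 9.1.3, comparing session-5 scores adjusted for session-1 values. It stands in the paragraph on the Dallas, SF-12 and STAI Y questionnaires, and VAS pain is not among the outcomes listed there.

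**The concern.** The primary comparison can be produced in three forms: unadjusted, adjusted for factors judged unbalanced, and adjusted for covariates picked partly on univariate results. The last two depend on choices made after the data are available. Selection on imbalance can pass over a strong prognostic factor that happens to look balanced. Selection on univariate results uses the outcome itself.

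Pain before the first session is the obvious prognostic factor. It is already recorded under 6.1.1, yet nothing guarantees that it enters any model for VAS pain. Taking the difference across each session does not do the same job, because it subtracts that session's own starting value and leaves the relation between initial pain and change unmodelled.

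The matter is practical in this trial. Practitioners are randomised (6.3) and then recruit their own patients (5.4), so they know the arm when they recruit. The feasibility survey (11.4) found 41 practitioners able to include such patients, or 41/3 = about 14 per arm. With so few clusters and open recruitment, groups may well differ at baseline, and adjusted and unadjusted results may then disagree. The plan should settle beforehand which one is read.

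**Working it through.** **The plan's own figures.** The plan gives no figure for adjustment. Its sizing figures in 9.2 are partly reproducible:
- 5%/3 = 1.67%, which matches the stated 1.7%.
- The repeated-measures factor for 5 sessions at correlation 0.5 is (1 + 4 × 0.5)/5 = 0.6.
- At two-sided 1.7% and 80% power, a 1-point difference with SD 1.5 needs 47 per group, and 47 × 0.6 = 28.2, so 29. A 1.5-point difference with SD 2.5 needs 58, and 58 × 0.6 = 34.8, so 35. These lie at or near the stated 30 to 40. Other corners of the stated ranges do not (8 to 79 overall).
- Design effect 1 + (m − 1) × ICC, with m = 3-5 (7.3) and ICC 0.05-0.2 (9.2), is 1.1-1.8. This turns 30-40 into 33-72, which contains 60. No dropout rate is given, so 60 is not uniquely determined.

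No covariate allowance appears in the sizing, so any gain from baseline adjustment comes on top of it.

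**Precision.** Assumed, because the documents do not give it: correlation r = 0.3-0.5 between session-1 pre-treatment VAS and the outcome. With m = 4, the variance of a group mean is proportional to m × ICC + (1 − ICC).

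*Baseline explains within-practitioner variance only.* The adjusted variance is m × ICC + (1 − ICC)(1 − r²).

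| ICC | Unadjusted | Adjusted, r = 0.3 | Adjusted, r = 0.5 | Worth in patients |
|---|---|---|---|---|
| 0.05 | 0.20 + 0.95 = 1.15 | 0.20 + 0.8645 = 1.0645 | 0.20 + 0.7125 = 0.9125 | 8% to 26% |
| 0.2 | 0.80 + 0.80 = 1.60 | 0.80 + 0.728 = 1.528 | 0.80 + 0.60 = 1.40 | 5% to 14% |

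*Baseline explains between-practitioner variance equally well.* The gain is 1/(1 − r²) − 1: 1/0.91 gives 10% and 1/0.75 gives 33%.

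So 60 adjusted patients are worth about 63 to 76 unadjusted ones in the first case (60 × 1.05, 60 × 1.26) and 66 to 80 in the second (60 × 1.10, 60 × 1.33).

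*Power, at the favourable end only.* Take 60 per group, design effect 1.3 (4 patients, ICC 0.1), a 1-point difference, two-sided 1.7%, one measure per patient, and the variance factor 0.75. Power goes from 0.79 to 0.91 (SD 1.5), 0.51 to 0.65 (SD 2) and 0.32 to 0.43 (SD 2.5).

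**Error rate.** Simulation with no treatment effect, 2,000 trials per setting. There were two arms of 15 practitioners with 4 patients each, ICC 0.05 or 0.2, and one summary value per patient. Candidates were baseline pain (correlation 0.3-0.7) and 10 other weakly prognostic covariates, matching the number of items in 8.2.1. Both selection rules were run at p < 0.20, which is assumed. Clinical judgement was not modelled.

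| Version | Rejection at nominal 5% |
|---|---|
| Unadjusted | 4.4-5.4% |
| Imbalance-adjusted | 1.5-3.6% |
| Fixed baseline pain | 4.5-5.9% |
| Smallest p of unadjusted, imbalance-adjusted and univariate-selected | 8.5-9.3% |

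The simulation error of a 5% rate is √(0.05 × 0.95/2000) = 0.5 percentage points, so the first and third rows agree with 5%. At nominal 1.7% the smallest-p rate was 2.4-3.4%. A separate simulation without clustering (8,000 trials, selection at p < 0.2 for univariate results and p < 0.1 for imbalance, covariates explaining 30% of variance) gave 8.3% for the smallest p, and 6.6% if they explain 10%.

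Baseline pain entered the imbalance-adjusted model in about 18-21% of runs and the univariate-selected model in 97-100%.

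**The case against.** The strongest reply is that the plan does have a hierarchy. Section 9.1.2 is headed as the main analysis and specifies one model without covariates, while the multivariable model is a supplement under secondary analyses. A reader might infer that several versions compete on equal terms for the main result, and the headings do not support that. What remains is narrower: 9.1.1 asks for both versions systematically, and no sentence says which one decides if they differ.

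A reader might also infer that covariates enter by univariate significance alone. The plan states no p-value, adds clinical relevance as a criterion, and judges imbalance on clinical grounds too. Baseline VAS could enter by that route, and in the simulation univariate selection nearly always admitted it. It is still not guaranteed, and the main model lacks it.

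A third inference would be that the trial's false-positive rate is about 8%. That figure requires someone to report the smallest of three p-values, which no passage permits.

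Session-1 pre-treatment VAS is also part of the session-1 outcome. That is no obstacle, because adjusting a change for its starting value is ordinary ANCOVA. For later sessions it is a covariate measured before any treatment.

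Finally, 9.3 refers to a statistical analysis plan with successive versions in the study file. A covariate list may exist there, but none is in the documents supplied.

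**Conclusion.** The point holds as one of specification and precision. The main model for pain omits baseline pain, the adjusted versions rest on covariates chosen after the data are seen, and the version that carries the conclusion is implied by headings but not stated.

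The main test as written keeps its level. The 8-9% error rate is conditional on reporting the most favourable version and on assumed thresholds. The firmer loss is precision: about 5-26% more patients if baseline VAS explains only within-practitioner variance, and 10-33% if it explains between-practitioner variance as well. Both ranges rest on an assumed correlation of 0.3-0.5, and the first also on 4 patients per practitioner and the plan's ICC of 0.05-0.2. Quoting 33% without that condition would ignore the clustering.

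Nor should adjustment be read as a cure for open recruitment. It does not remove selection on unmeasured features by practitioners who know their arm.

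**What to change.** - **9.1.2:** add session-1 pre-treatment VAS as a fixed covariate in the main mixed model for pain variation, alongside group, session, their interaction, and the patient and practitioner random effects. State that this model gives the primary result, and keep the unadjusted model as a sensitivity analysis.
- **9.1.1 and 9.1.3:** replace the imbalance-triggered and univariate selection rules with covariates named before the data are seen, and label those models as sensitivity analyses. Duration of low back pain (listed in 8.2.1) is one candidate. STarT Back is another only if its score is confirmed as recorded: 5.1 uses it at inclusion, but neither 6.1.2 nor 8.2.1 lists it. No passage identifies either as prognostic for pain change, so the choice belongs to the trial team.

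The cost is one extra model parameter and SAP wording. The baseline VAS is already collected.

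### Start-to-end comparisons of the Dallas, SF-12 and one STAI score use patient-level tests although practitioners are randomised

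*Combined protocol and SAP*

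**What the plan says.** Section 6.3 randomises practitioners to the three groups and places all patients of a practitioner in the same group. Section 7.3 expects 3 to 5 patients per practitioner.

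For the quantitative secondary scores (Dallas, SF-12, STAI Y), section 9.1.3 states that the comparisons between groups "will be carried out using Student's t test or the non-parametric Mann-Whitney test if the conditions of Student's test are not met". For the same scores put into categories, the comparisons "will be performed by chi-square test or Fisher's exact test", and "The results will be expressed in terms of absolute difference and 95% confidence interval".

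Other text bears on these comparisons:

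- Section 9.1.1: "Comparisons between randomisation groups will be made systematically (1) without adjustment (2) by adjusting for factors whose distribution could be unbalanced between groups".
- Section 9.1.3, in the paragraph on the covariate-adjusted model for the primary endpoint: "The practitioner effect will be measured and taken into account in the statistical analyses as a random effect".
- Section 9.1.3, for the start-to-end scores: "an ANCOVA-type analysis will also be proposed in order to compare the scores at the 5th session", adjusting for session 1. No practitioner term is named.
- Section 9.1.3, for the categorised scores: "In multivariate situations, mixed generalized linear regression models (logit link function) will be considered". No random effect is named.

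On anxiety, section 6.1.2 has STAI YA completed at every session and YB at sessions 1 and 5. Section 9.1.3 describes YB as the per-session scale and gives it the primary endpoint's repeated-measures model.

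**The concern.** Student, Mann-Whitney, chi-square and Fisher tests on individual patients assume that patients are independent. Here patients are grouped by practitioner and the practitioner is what was randomised, so any practitioner-level variation adds to the variance of the difference between groups, and these tests ignore it. They cannot carry a random effect, so the general sentence on the practitioner effect cannot rescue them.

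The plan recognises clustering elsewhere: in the primary model (section 9.1.2), in the longitudinal categorical models (section 9.1.3) and in the sample size (section 9.2). The start-to-end comparisons are the exception.

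Function and quality of life are named in the secondary objectives (section 3.2) and are measured only at sessions 1 and 5, so no repeated-measures model covers them. If their scores correlate within practitioner, the intervals are too narrow and Student, Mann-Whitney and chi-square reject too often. Because of the YA/YB conflict, one cannot tell which anxiety scale is left to the simple tests.

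**Working it through.** **Inputs.** Patients per practitioner m = 3 to 5 (section 7.3). Patients per group: 60 (section 9.2). ICC 0.05 to 0.2 (section 9.2, given when sizing for pain; applying it to these scores is an assumption, because the documents give no ICC for them). Test level 5% (section 9.1.1; two-sided assumed). Practitioners able to include patients: 41 (section 11.4), which for 180 patients gives 180/41 = 4.4 each. The plan states no error rate or sample size for the secondary scores, so there is no figure of its own to reproduce.

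**Step 1, design effect.** DE = 1 + (m − 1) × ICC. Lowest: 1 + 2 × 0.05 = 1.10. Highest: 1 + 4 × 0.2 = 1.80. At the high end, 60 patients carry the information of 60/1.80 = 33 independent ones.

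**Step 2, true error of a nominal 5% Student-type test.** α = 2 × [1 − Φ(1.96/√DE)]; the coverage of the 95% interval is 1 − α.

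| m | ICC 0.05 | ICC 0.1 | ICC 0.2 |
|---|---|---|---|
| 3 | 6.2% | 7.4% | 9.8% |
| 4 | 6.8% | 8.6% | 12.1% |
| 4.4 (41 practitioners) | 7.0% | 9.0% | 13.0% |
| 5 | 7.4% | 9.8% | 14.4% |

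Coverage runs from 93.8% down to 85.6%. At ICC 0.01 the error is only 5.2% to 5.5%.

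**Step 3, simulation with no true effect.** Two groups of 60, as 20 × 3, 15 × 4 or 12 × 5 practitioners × patients, ICC 0.05 to 0.2; 20,000 trials per setting (5,000 for Mann-Whitney). Categorised scores are the underlying score cut at its median, so 50% prevalence; the ICC is that of the underlying score.

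| Test | Rejection, ICC 0.05 to 0.2 | Rejection, ICC 0 |
|---|---|---|
| Student | 6.2% to 14.3% | about 5% |
| Mann-Whitney | 5.9% to 14.8% | about 5% |
| Chi-square | 6.2% to 11.9% | 5.6% to 5.8% |
| Fisher | 4.3% to 8.6% | 3.6% to 3.7% |

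The interval for the absolute difference covers 93.8% to 88.1%, against 94.2% to 94.4% without clustering. Independent repeats agreed to within about one percentage point. Fisher passes 5% only at ICC 0.1 with 4 or 5 patients per practitioner, or at ICC 0.2.

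**Step 4, do cluster-aware analyses repair it?** Same settings. A t-test on practitioner means rejects 4.7% to 5.2%, and so does a comparison of practitioner-level proportions. A mixed ANCOVA fitted by REML, with a random practitioner intercept and t on 2k − 2 degrees of freedom (k practitioners per group), rejects 3.6% to 4.9% (6,000 trials). A permutation test over practitioners on skewed, baseline-adjusted scores rejects 4.4% to 5.3%, against 6.2% to 14.9% for Mann-Whitney on skewed session-5 scores (4,000 trials).

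**The case against.** The case for leaving the plan alone has four parts.

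*Clustering is partly handled.* The practitioner sentence speaks of the statistical analyses in general, and an ANCOVA and mixed logit models stand beside the simple tests. This stands in part: whether those models carry a practitioner effect is a gap in wording, not a proven unclustered analysis. But the ANCOVA comes in addition to the tests, the mixed logit is only a possibility in multivariable settings, and the four named tests cannot hold a random effect.

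*Section 9.1.1 does not require unclustered tests.* Its unadjusted step concerns covariates, and a mixed model without covariates would satisfy it. That is correct. The prescription of the tests comes from section 9.1.3, and it is explicit there.

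*The sizes are near the unfavourable end.* For the categorised scores this largely stands. The plan leaves the thresholds open, and away from a median split the excess shrinks: chi-square rejects 5.8% to 9.9% at 20% prevalence and 5.5% to 8.7% at 10%. Fisher stays at 2.3% to 4.6% at 10% prevalence and 1.2% to 2.0% at 5%, so where it would usually be chosen it does not exceed its level. For the quantitative scores, three patients per practitioner would need 180/3 = 60 practitioners against 41 available. The 41-practitioner row is therefore the more realistic one, and its range of 7.0% to 13.0% has a higher lower end.

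*The endpoints are secondary.* Section 9.1.1 says: "Part of the analyses concerning the secondary evaluation criteria should be mainly exploratory in nature". That limits the consequence, but only part of the analyses is so described, and an exploratory label does not make an interval reach its stated coverage.

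**Conclusion.** The concern holds. The named start-to-end tests ignore the unit of randomisation. For the quantitative scores the true error of a nominal 5% test is 6.2% to 14.4%, or 7.0% to 13.0% with 41 practitioners, provided the ICC assumed when sizing for pain carries over to these scores. If the ICC is nearer 0.01, the effect is negligible. For categorised scores the excess is smaller and depends on the cut-point; Fisher's test exceeds 5% only for common categories with stronger clustering.

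The primary analysis, the per-session anxiety analysis and the longitudinal categorical models include the practitioner effect, so the main conclusion of the trial is not at risk. This should be fixed before the analysis.

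**What to change.** 1. **Quantitative start-to-end scores.** Make the session-5 ANCOVA of section 9.1.3 the main analysis: a linear mixed model on group and session-1 score, with a random practitioner intercept and small-sample degrees of freedom. If residuals are clearly non-normal, use a permutation test over practitioners in place of the patient-level Mann-Whitney test.
2. **Categorised scores.** Replace chi-square and Fisher, also for the unadjusted comparison, with the mixed logit model and its random practitioner effect named, or with a comparison of practitioner-level proportions. The latter also gives the absolute difference that the plan wants to report.
3. **Anxiety.** Reconcile sections 6.1.2 and 9.1.3 on STAI YA and YB, so that the scale measured only at start and end also gets a mixed or practitioner-level analysis.

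**Cost.** SAP wording and a little more code; no new data. Unadjusted intervals widen by the factor √DE × t(0.975; 2k − 2)/t(0.975; 118), with k = 60/m:

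- m = 3, ICC 0.05: √1.10 × 2.024/1.980 = 1.072, or 7% wider.
- m = 5, ICC 0.2: √1.80 × 2.074/1.980 = 1.405, or 41% wider.
- 41 practitioners: 12% to 35% wider.

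Adjusting for the session-1 score recovers part of this. With an assumed correlation of 0.5, the factor √(1 − 0.5²) = 0.866 gives 1.072 × 0.866 = 0.93 to 1.405 × 0.866 = 1.22. Simulating the fitted REML model gives intervals about 5% to 6% narrower to 22% wider than the patient-level Student interval.

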9.1.4 Method for taking into account missing, unused or invalid data

A sensitivity analysis will be carried out to study the attrition bias, i.e. the quantity (level of attrition) and nature (independence from the randomisation group) of the missing data, and to propose the most appropriate data imputation method if necessary.

9.2 Justification of the number of subjects / power analysis.

In order to evaluate the specific benefits of fasciatherapy compared with physiotherapy for chronic low back pain in terms of variation in pain before and after each of the 5 sessions considered in this protocol, the estimate of numbers is based on recruitment capacity, the time required for experimentation and simulations concerning the effect size for risks of error of 1st and 2nd kind fixed respectively at 1.7% (two-sided with correction for multiple comparisons: group receiving only conventional physiotherapy, group receiving conventional physiotherapy and fasciatherapy) and less than 20%.

Thus, if we estimate that a clinically relevant difference in pain assessment is between 1 and 2 points, for a standard deviation of the variation in pain of 1.5 to 2.5 points, we should include 30 to 40 patients for a statistical power of over 80% and an intra-individual correlation coefficient (5 sessions per subject) conventionally set at 0.5.

This proposal must be revised upwards in order to take into account the dropouts inherent in this type of protocol and the inter- and intra-practitioner variability (due to the experimental design of the cluster trial) which can be measured by the intra-class correlation coefficient and which it seems reasonable to estimate in the context of this project to be of the order of 0.05 to 0.2. It is therefore proposed to include 60 patients in each of the study groups.

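### Pre-tests of normality and variance decide which hypothesis is tested for the secondary scores, and nothing says that the baseline-adjusted analysis leads

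*Combined protocol and SAP*

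**What the plan says.** For the Dallas, SF-12 and STAI Y scores, section 9.1.3 plans Student's t-test, or Mann-Whitney "if the conditions of Student's test are not met (normality verified by the Shapiro-Wilk test and equality of variances by the Fisher-Snedecor test". A failed variance test is therefore enough, on its own, to lead to Mann-Whitney. No unequal-variance t-test is named. Part of the sentence is printed twice, and the first copy ties Mann-Whitney to the conditions being met; I read that as a drafting slip and do not count it.

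Results are to be given as an effect size with a 95% confidence interval. The section then adds that "an ANCOVA-type analysis will also be proposed in order to compare the scores at the 5th session", adjusting for session 1, and that "Where appropriate, the above analyses may be supplemented by more appropriate generalised linear regressions". It does not say which result leads.

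The context is as follows.
- Section 9.1.1: "All statistical tests will be carried out with a risk of error of the first kind α of 5" per cent. It also plans medians for non-normal variables, promises comparisons both unadjusted and adjusted for unbalanced factors, and calls part of the secondary analyses mainly exploratory.
- Section 9.2: "It is therefore proposed to include 60 patients in each of the study groups", with a practitioner intra-class correlation (ICC) of 0.05 to 0.2.
- Section 7.3: 3 to 5 patients per practitioner.
- Section 6.1.2: STAI YA at every session, YB at sessions 1 and 5. Section 9.1.3 instead has YB completed at every session and sends it to the mixed model used for pain.

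**The concern.** Mann-Whitney is a test of a shift in location only when the two distributions have the same shape. Unequal variance breaks that condition. The plan thus looks for unequal spread and, on finding it, picks a test that does not compare means in that situation. The choice is made on the trial's own data, so one scale may be tested on means and another on ranks. If the pre-tests are run for each pair of arms, the same could happen between two contrasts on one scale. The promised effect size and interval need not agree with a rank-based p-value.

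This bears on section 3.2, which wants to show benefit on anxiety, function and quality of life and to identify the aspect on which fasciatherapy works best. Ranking aspects needs one kind of comparison on all scales. Meanwhile the ANCOVA, which needs no switch and is more precise, has no stated priority, so each scale can yield two answers.

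**Working it through.** **Inputs from the plan.** 60 patients per arm, tests at 5% (taken as two-sided), ICC 0.05 to 0.2, 3 to 5 patients per practitioner (4 used, so 60/4 = 15 practitioners per arm). Dropout is expected ("in order to take into account the dropouts inherent in this type of protocol") but no rate is given.

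**Assumptions.** Distributions, SD ratios and baseline correlations of the secondary scores are not in the plan. All are assumed below.

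**1. Nominal level.** The 5% is a set level, so there is no derived figure to reproduce. The rule was simulated as written: Shapiro-Wilk in each arm and the F test, each at 5%; Mann-Whitney if any is significant, otherwise pooled t. With normal data and equal SDs it should switch in about 1 − 0.95³ = 14.3% of trials; simulation gave 14%. With equal spreads, across the distributions tried, the rule rejected in 4.6% to 5.3% of trials. The 5% level is then met.

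**2. Equal means, unequal spread, no clustering** (4,000 to 6,000 trials per case; Monte Carlo margin near 5% is about ±0.7 points at 4,000):

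| Scores and arms | SD ratio | Rule rejects | Welch t |
|---|---|---|---|
| Normal, 60/60 | 1.5 | 5.0% to 6.3% over repeated runs | about 5% |
| Normal, 60/60 | 2 | 5.7% to 6.3% | about 5% |
| Normal, 60/60 | 3 | 7.7% | 5.3% |
| Normal, 60/45, larger SD in smaller arm | 2 | 6.6% | 5.1% |
| Gamma, mean 40, SD 18 v 15 or same ratio | 1.2 | 5% to 6% | about 5% |
| Gamma, mean 40, SD 20 v 15 | 1.33 | about 7% | about 5% |
| Gamma, mean 40, SD 25 v 15 | 1.67 | about 15% | about 5% |
| Gamma, mean 40, SD 30 v 15 | 2 | about 25% | 5% to 6% |
| Exponential shape (extreme skew) | 2 | 44.7% | 5.4% |

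In the gamma cases with SD 25 v 15 and 30 v 15, Shapiro-Wilk causes almost every switch; the F test alone does so in roughly 2% of trials or fewer. For normal scores the F test is the usual route (88% of trials go to Mann-Whitney at ratio 1.5), and there the excess is small.

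**3. What the large figures measure.** A gamma score with mean 40 has shape (40/SD)². SD 15 gives shape 7.11 and median 38.1; SD 25 gives 2.56 and 34.9; SD 30 gives 1.78 and 32.8. The means are equal but the medians are not, so these rejections are errors only if the mean is the target.

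**4. Mixed tests on one scale.** If the pre-tests are run pair by pair, with normal scores and 60 per arm, Group 2 v 1 and Group 3 v 1 receive different tests in about 16% of trials when all SDs are equal. The figure is about 40% when one experimental arm's SD is 1.25 times the others.

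**5. Clustering.** The design effect is 1 + (4 − 1) × ICC, which is 1.15 at 0.05 and 1.60 at 0.2. An unadjusted test then has an effective critical value of 1.96/√1.15 = 1.83 or 1.96/√1.60 = 1.55, so it rejects about 6.8% or 12.1% under the null. Simulation gave 6.8% and 12.3% for t, and 6.7% and 11.9% for Mann-Whitney. An ANCOVA without a practitioner term rejected 7% to 11% over the same ICC range; with practitioner-clustered standard errors, 5% to 6%.

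**6. Precision of the ANCOVA.** With session-1 to session-5 correlation r, the ANCOVA variance is (1 − r²) times that of an unadjusted session-5 comparison: 0.75 at r = 0.5 and 0.51 at r = 0.7, a saving of 25% to 49%. Against change scores the ratio is (1 − r²)/[2(1 − r)] = (1 + r)/2: 0.75 and 0.85, a saving of 25% to 15%.

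**The case against.** Four replies have weight.

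- **The rank test answers its own question.** The skewed arms in step 2 differ in median, and Mann-Whitney detects that. Section 9.1.3 names no target of estimation and section 9.1.1 plans medians for non-normal variables. This stands. A reader might infer that arms with the same typical level will be declared different because of spread alone; the large figures do not show that.
- **The inputs are chosen.** SD ratios of 1.7 to 2 between three arms that all receive active care come from no source in the plan. At ratio 1.2 even gamma scores give only 5% to 6%. This stands, and it limits the size of the point.
- **Much is already planned.** The ANCOVA is there, optional regressions are there, and part of the secondary analysis is exploratory. This stands in part: only a part is exploratory, 5% is set for all tests, and nothing ranks the analyses.
- **A random practitioner effect is mentioned in section 9.1.3.** It appears in the paragraph that extends the primary endpoint model. It could be read to cover the ANCOVA, although the ANCOVA sentence does not say so. The t-test and Mann-Whitney as described have no place for it.

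Two further inferences go beyond the text. The plan does not say that the pre-tests are run pair by pair; that follows only if two-sample tests are applied to three arms in the obvious way. Nor can trait anxiety be listed firmly as affected, because sections 6.1.2 and 9.1.3 disagree on which STAI form is taken at each session.

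**Conclusion.** The point holds as one of method choice. The pre-tests let the data select the hypothesis, Mann-Whitney is the wrong remedy for unequal variance if means are to be compared, and no rule gives the better analysis priority.

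The documents do not support a claim of general, serious false-positive inflation from the switch. For a comparison of means at 60 per arm the excess is negligible to small with symmetric scores. It reaches about 15% to 25% only under assumed gamma skew combined with SD ratios of 1.7 to 2. Over the plan's own ICC range, ignoring clustering takes the rate to about 7% to 12% with no assumption about skew or unequal spread, so replacing the switch by Welch's test alone would not be enough. The primary endpoint is not affected.

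**What to change.** In section 9.1.3:

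1. Delete the Shapiro-Wilk and Fisher-Snedecor switch.
2. Name the ANCOVA of session-5 scores adjusted for session 1 as the leading analysis for each scale. Fit one three-arm model for all contrasts, with a random practitioner effect (or practitioner-clustered standard errors with a small-sample correction, given about 15 practitioners per arm) and residual variance allowed to differ by arm.
3. Report mean differences in scale points with 95% confidence intervals.
4. Keep rank tests only as a labelled sensitivity check.
5. State which STAI form follows this rule and which follows the repeated-measures model, and reconcile section 6.1.2 with section 9.1.3.

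The cost is SAP wording. The session-1 and session-5 scores are already collected, the practitioner is already a random effect in the pain model, and the change reduces the number of competing analyses.
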